## **STATISTICAL ANALYSIS PLAN VERSION HISTORY**

This Statistical Analysis Plan (SAP) was developed based on Roche SAP model document V 3.0.

SAP Version	Approval Date	Based on Protocol (Version, Approval Date)
1	See electronic date stamp on the last page of this document	V 2.0, 2 Feb 2024

## LIST OF ABBREVIATIONS AND DEFINITIONS OF TERMS

Abbreviation or Term	Description
AE	Adverse Event
AESI	Adverse Event of Special Interest
ALT	alanine aminotransferase
AST	aspartate aminotransferase
BID	twice a day
BMI	Body Mass Index
CRF	Case Report Form
EC 50	50% effective concentration
FAS	Full Analysis Set
FASi	Full Analysis Set-infected participants
IxRS	Interactive Voice/Web-Based Response System
LLoD	Lower Limit of Detection
LLoQ	Lower Limit of Quantification
NCI CTCAE	National Cancer Institute Common Terminology Criteria for Adverse Events
PK	pharmacokinetic
PKAS	pharmacokinetic analysis set
PT	preferred term
SAE	Serious Adverse Events
SAP	Statistical Analysis Plan
SAS	Safety Analysis Set
SOC	system organ class
TEAEs	treatment-emergent adverse events
TTAS	time to alleviation of influenza signs and symptoms

## 1. INTRODUCTION

The analyses described in this Statistical Analysis Plan (SAP) will supersede those specified in Protocol YV44465 for the purposes of a regulatory filing.

The objective of this study is to evaluate the safety, pharmacokinetics, and efficacy of baloxavir marboxil in Chinese pediatric participants aged 1 to <12 years with influenza symptoms.

There are no changes to the planned analyses described in the protocol.

### 1.1 TRIAL OBJECTIVES, ENDPOINTS, AND ESTIMANDS

**Table 1 Primary and Secondary Objectives and Corresponding Estimand**

Safety (Primary) Objective	Estimand Definition

To describe the safety of a single dose of baloxavir marboxil compared with 5 days of oseltamivir administered BID in Chinese pediatric participants

	

Population: All participants aged 1 to <12 years with influenza symptoms who received at least 1 dose of study treatment

Endpoint:

Incidence, severity, and timing of adverse events, serious adverse events, with severity determined according to NCI CTCAE v5

Change from baseline in vital sign measurements

Change from baseline in clinical laboratory test results

Treatment:

Experiment arm: baloxavir marboxil single dose

Control arm: oseltamivir 5 days BID

Intercurrent events and handling strategies

Treatment discontinuation: treatment policy strategy

Rescue medication: treatment policy strategy

Population-level summary:

No formal statistical testing will be conducted. Analyses will be descriptive.

Incidence of adverse events, serious adverse events by System Organ Class, by Preferred Term and by worst severity

Change from baseline summaries will be presented overall and by treatment with use of descriptive statistics, including means, standard deviations, medians, and ranges for continuous variables

**Table 1 Primary and Secondary Objectives and Corresponding Estimand (cont.)**

Efficacy (Secondary) Objective	Estimand Definition

 
To describe the clinical efficacy of baloxavir marboxil compared with oseltamivir in Chinese pediatric participants
 
	
 
Population: All participants aged 1 to <12 years with influenza symptoms who received at least 1 dose of study treatment who have had a laboratory confirmation of influenza infection (PCR result) from any swab sample collected at baseline or during the study
 
Endpoints: 
 
Time to alleviation of influenza signs and symptoms, defined as the length of time taken from the start of treatment to the point at which all of the following criteria are met and remain so for at least 21.5 hours: 
 
A score of 0 (no problem) or 1 (minor problem) for cough and nasal symptoms (Items 14 and 15 of the CARIFS, see Appendix 1.
 
A "yes" response to the following question on the CARIFS: "Since the last assessment has the subject been able to return to day care/school (if applicable), or resume his or her normal daily activity in the same way as performed prior to developing the flu?" (if possible).
 
Return to afebrile state (tympenic temperature <math>\leq 37.2^{\circ}\text{C}</math>).
 
 
 
Duration of fever (time to return to afebrile state [tympenic temperature <math>\leq 37.2^{\circ}\text{C}</math>] and remaining so for at least 21.5 hours)
 
Duration of symptoms (alleviation of all symptoms as defined by a score of 0 [no problem] or 1 [minor problem] and remaining so for at least 21.5 hours, for all 18 symptoms specified in the CARIFS questionnaire)
 
Time to return to normal health and activity based on the CARIFS questionnaire
 
Frequency of influenza-related complications (death, hospitalization, radiologically confirmed pneumonia, bronchitis, sinusitis, otitis media, encephalitis/encephalopathy, febrile seizures, myositis)
 
Proportion of participants requiring antibiotics for influenza related complications
 
 
 
Treatment: 
 
Experiment arm: baloxavir marboxil single dose
 
Control arm: oseltamivir 5 days BID
 
 
 
Intercurrent events and handling strategies 
 
Treatment discontinuation: treatment policy strategy
 
 
 


**Table 1 Primary and Secondary Objectives and Corresponding Estimand (cont.)**

Efficacy (Secondary) Objective	Estimand Definition
	
 
– Rescue medication: treatment policy strategy
 
• Population-level summary: No formal statistical testing will be conducted. Analyses will be descriptive. Time to event endpoints and duration endpoints will be summarized with use of Kaplan Meier plots and median survival time for each treatment arm.
 

Virology (Secondary) Objective	Estimand Definition

 
• To evaluate the virological activity of baloxavir marboxil compared with oseltamivir in Chinese pediatric participants
 
	
 
• Population: All participants aged 1 to <12 years with influenza symptoms who received at least 1 dose of study treatment who have had a laboratory confirmation of influenza infection (PCR result) from any swab sample collected at baseline or during the study
 
• Endpoints: 
 
– Time to cessation of viral shedding by virus titer and by RT-PCR with use of samples from respiratory swabs
 
– Change from baseline in influenza virus titer and in the amount of virus RNA (RT-PCR) at each timepoint with use of samples from respiratory swabs
 
– Proportion of participants with positive influenza virus titer and proportion of participants positive by RT-PCR at each timepoint with use of samples from respiratory swabs
 
– Area under the curve in virus titer and in the amount of virus RNA (RT-PCR) with use of samples from respiratory swabs
 
 
 
• Treatment: 
 
– Experiment arm: baloxavir marboxil single dose
 
– Control arm: oseltamivir 5 days BID
 
 
 
• Intercurrent events and handling strategies 
 
– Treatment discontinuation: treatment policy strategy
 
– Rescue medication: treatment policy strategy
 
 
 
• Population-level summary: Summaries will be presented overall and by treatment with use of descriptive statistics, including means, standard deviations, medians, and ranges for continuous variables and proportions for categorical variables Time to event endpoints will be summarized with use of Kaplan Meier plots and median survival time.
 

BID = twice a day; CARIFS = Canadian Acute Respiratory Illness and Flu Scale; NCI CTCAE = National Cancer Institute Common Terminology Criteria for Adverse Events; PCR = polymerase chain reaction; RT-PCR = reverse transcriptase polymerase chain reaction.

**Table 2 Other Secondary Objectives and Endpoints**

Pharmacokinetic (Secondary) Objective	Corresponding Endpoints

 
To describe the PK of baloxavir after single-dose administration of baloxavir marboxil in Chinese pediatric participants
 
	
 
Plasma concentrations of baloxavir (RO7191686, active metabolite) will be summarized by time (<math>C_{24}</math> and <math>C_{72}</math>) and body weight group (<math><20</math> kg and <math>\geq 20</math> kg)
 
Population PK model derived parameters (e.g., <math>AUC_{inf}</math>, <math>C_{max}</math>, and other PK parameters as appropriate) (modeling report)
 

Virology (Secondary) Objective	Corresponding Endpoints

 
To evaluate the polymorphic and treatment-emergent amino acid substitutions in the PA gene and drug susceptibility in participants with evaluable virus in Chinese pediatric participants
 
	
 
Polymorphic and treatment-emergent amino acid substitutions in the PA gene
 
Drug susceptibility in participants with evaluable virus
 

Palatability (Secondary) Objective	Corresponding Endpoint

 
To evaluate the palatability of the oral suspension
 
	
 
Proportion of participants reporting each palatability and acceptability response (see Appendix 3)
 

$AUC_{inf}$  = area under the concentration-time curve extrapolated to infinity;  $C_{24}$  = concentration at 24 hours postdose;  $C_{72}$  = concentration at 72 hours postdose;  $C_{max}$  = maximum observed concentration; PK = pharmacokinetic;  $t_{1/2}$  = elimination half-life;  $T_{max}$  = time of maximum observed concentration.

## 1.2 STUDY DESIGN

This is a multicenter, randomized, open-label, active-controlled (i.e., oseltamivir) study to assess the safety, pharmacokinetics, and efficacy of baloxavir marboxil compared with oseltamivir in Chinese pediatric participants aged 1 to  $<12$  years with influenza symptoms within 48 hours of symptom onset.

Approximately 100 pediatric participants are planned to be enrolled. Of the overall sample size, approximately 1/3 participants who are 1 to  $<5$  years old and 2/3 participants who are 5 to  $<12$  years old are planned to be enrolled.

Participants will be screened and randomized on Day 1 and assigned in a 2:1 ratio to receive a single oral dose of baloxavir marboxil based on body weight (2 mg/kg for participants weighing  $<20$  kg or 40 mg for participants weighing  $\geq 20$  kg to  $<80$  kg or 80 mg for those weighing  $\geq 80$  kg) for oral suspension or oseltamivir (twice a day dose based on body weight) for 5 days. Re-screening of participants who fail to meet the inclusion and exclusion criteria will not be permitted for the same illness.

episode, as the time from symptom onset to the treatment window is limited to 48 hours. Either drug will be started at the time of randomization.

The total study duration for each participant will be 29 days, consisting of a 5-day treatment period (mandatory visits on Days 1, 2, and 4) and a 24-day follow-up period (mandatory visits on Days 6, 10, and 29). For the following assessments at clinic visits: physical examinations, vital signs, adverse events, concomitant therapies, clinical laboratory tests, and nasal/throat swabs. Visits on Day 29 or early termination visits can be conducted remotely. Throughout the treatment follow-up periods, the parents/caregivers will maintain a participant diary for each participant in order to record body temperatures (tympanic assessment), influenza symptoms, and acetaminophen use.

Temperatures will be recorded as follows:

- Days 1–3: 4 times daily (morning, noon, evening, and bedtime);
- Days 4–9: twice a day (morning and evening);
- Days 10–15: once daily.

Influenza symptoms will be recorded as follows:

- Days 1–9: twice a day (morning and evening)
- Days 10–15: once a day.

### **1.2.1 Treatment Assignment**

This is a randomized, open-label study. After initial written informed consent has been obtained, all screening procedures and assessments have been completed, and eligibility has been established for a participant, the study site will obtain the participant's identification number and treatment assignment from an Interactive Voice/Web-Based Response System (IxRS).

Participants will be randomly assigned in a 2:1 ratio to one of the two treatment arms: a single oral dose of baloxavir marboxil or oseltamivir. Randomization will be stratified by age group (1-<5 years old versus 5-<12 years old) and high risk factors for influenza complications (with versus without), see [Appendix 2](#).

### **1.2.2 Independent Review Facility**

No Independent Review Facility is planned for this study.

### **1.2.3 Data Monitoring**

No Data Monitoring Committee is planned for this study.

## **2. STATISTICAL HYPOTHESES AND SAMPLE SIZE DETERMINATION**

### **2.1 STATISTICAL HYPOTHESES**

No formal statistical hypotheses will be tested for this study.

### **2.2 SAMPLE SIZE DETERMINATION**

No formal sample-size calculations were performed. Approximately 100 pediatric participants (67 participants in the baloxavir marboxil treatment group and 33 participants in the oseltamivir treatment group) are planned to be enrolled.

The sample size of 67 participants in the baloxavir marboxil treatment group will provide a probability of 87% to detect an adverse event with a 3% incidence rate for at least 1 participant. The given sample size provides a probability of at least 1 participant experiencing an adverse event with a true incidence rate from 1%–5% as shown in [Table 3](#).

**Table 3 Probability of Adverse Events by Incidence Rates**

	True Incidence Rate of an Adverse Event				
	1%	2%	3%	4%	5%
Probability of at least 1 participant experiencing an adverse event	49%	74%	87%	94%	97%

Of the planned overall sample size, approximately 1/3 participants aged 1 to <5 years old and 2/3 participants aged 5 to <12 years old are planned to be enrolled.

The number of participants in this study will be monitored on an ongoing basis in order to ensure an adequate number of specific participants are enrolled (e.g., participants with high risk factors for influenza complications and participants meeting the definition of full analysis set-infected participants (FASi).

Note: Sparse Pharmacokinetic (PK) samples from at least 48 pediatric participants in the baloxavir group will be collected to ensure at least 40 pediatric participants' samples are available for analysis. The sample size is determined to reach approximately 10% of the overall pediatric population which are included in the population PK model.

## **3. ANALYSIS SETS**

The participant analysis sets for the purposes of analyses are defined in [Table 4](#)..

**Table 4 Participant Analysis Sets**

Participant Analysis Set	Description
FAS	All randomized participants; participants will be included in the analyses according to the treatment to which they were assigned.
FASi	A subset of FAS participants who received at least 1 dose of study treatment and had a laboratory confirmation of influenza infection (PCR result) from any swab sample collected at baseline or during the study; participants will be analyzed according to the treatment to which they were assigned.
SAS	All participants who received at least 1 dose of study treatment; participants will be analyzed according to the treatment that they actually received.
PKAS	All participants with evaluable PK samples from the baloxavir marboxil arm (i.e., who received baloxavir marboxil).

FAS = full analysis set; FASi = full analysis set-infected participants; PCR = polymerase chain reaction; PK = pharmacokinetic; PKAS = pharmacokinetic analysis set; SAS = safety analysis set.

## **4. STATISTICAL ANALYSES**

### **4.1 GENERAL CONSIDERATIONS**

The statistical analyses of safety, pharmacokinetics and efficacy will be descriptive. The Safety Analysis Set (SAS) will be used for all analyses on primary endpoints and analyses of secondary efficacy and virology endpoints will be conducted on the FASi. The PK analysis set (PKAS) will be used for the PK analyses.

#### 4.1.1 Visit Windows

**Table 5 Acceptable Time Windows for Parameters Other Than Data from the Patient Diary**

Time Point	Acceptable Time Window
(Scheduled Time Point)	
Pre-dose at Visit 1 (Day 1)	Before dosing on Day 1
Post-dose at Visit 1 (Day 1)	Between 0.5 and 4 hours after dosing (on Day 1)
Visit 2 (Day 2)	Day 2
Optional Visit 1 (Day 3)	Day 3
Visit 3 (Day 4)	Day 4
Visit 4 (Day 6)	Between Day 5 and Day 7 as follows: 

• if patient presents on Day 5 with no Day 4, and no Day 6 this will be classed as Visit 4.

• if patient presents on Day 5 with no Day 4, and Day 6 this will be classed as Visit 3.

• if patient presents on Day 5 with Day 4 and no Day 6 this will be classed as Visit 4.

Visit 5 (Day 10)	Between Day 8 and Day 12
Optional Visit2 (Day 15)	Between Day 13 and Day 22
Visit 6 (Day 29)	On or after Day 23
Withdrawal	Date of withdrawal + 14 days

\* if time is missing for data collected on Visit 1 where, per the schedule of activities, this data should be collected at 'v1 screening' or 'v1 post-dose' it is defined as 'Pre-dose at Visit 1 (Day 1)' or 'Post-dose at Visit 1 (Day 1)' respectively.

Measurements collected within the acceptable time window for each scheduled assessment time point, including data obtained at the time of withdrawal, will be used for the analyses of all endpoints at each assessment time point. For all patients with multiple values within a visit window, the value obtained closest to the target time point will be used. If two measurements collected with the same time deviation exist before and after the target time point, the measurement obtained before the target time point will be adopted for analysis. The assessment time point having no measurements within the corresponding acceptable time window will be considered as missing.

For summaries of data not collected by visit, such as adverse events, medical history and concomitant medications, all data up to the study completion/discontinuation date will be included.

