- ^j The parent/caregiver will complete the CARIFS questionnaire twice a day (morning and evening) on Days 1–9 and then once a day on Days 10–15. The results will be recorded in the participant diary.
- ^k A complete physical examination will be conducted at screening. Limited, symptom-directed physical examinations will be performed postdose. Height and body weight will be measured at screening only.
- ^l Conduct assessment if the investigator determines that influenza symptoms or viral shedding are persisting or at the investigator's discretion.
- ^m Vital signs will be recorded if abnormal physical examination findings or adverse events are recorded since the last visit or at the investigator's discretion on Day 29.
- ⁿ *Respiratory samples will be collected using nasopharyngeal or nasal swabs. At each swab timepoint, a virology test will be performed by the central laboratory.*
- ^o PK samples will be collected in baloxavir marboxil treated participants and sent to a central laboratory.

Table 1 Schedule of Activities (cont.)

-
- ^p PK samples will be collected at Day 1 (1 sample between 0.5 and 2 hours postdose). Participants will be assigned to have either the Day 2 (24 hours postdose) or the Day 4 sample (72 hours postdose). Only 1 sample from Days 6–10 is required and can be collected at either Visit 4 or Visit 5.
- ^q After informed consent has been obtained but prior to initiation of study treatment, only serious adverse events caused by a protocol-mandated intervention should be reported. After initiation of study treatment, all adverse events will be reported until 28 days after the first dose of study treatment. After this period, the Sponsor should be notified if the investigator becomes aware of any serious adverse event that is believed to be related to prior exposure to study drug (see [Appendix 3](#)).

Table 2 Schedule of Pharmacokinetic Samples

| Visit Day | Timepoint | Sample Type |
|--------------------|---|--------------------|
| Day 1 | One sample between 0.5 and 2 hours postdose | Drug PK (plasma) |
| Day 2 ^a | 24 hours postdose | Drug PK (plasma) |
| Day 4 ^a | 72 hours postdose | Drug PK (plasma) |
| Days 6–10 | Only 1 sample is to be collected at visit Day 6 or Day 10 | Drug PK (plasma) |

PK=pharmacokinetic.

^a Participants will be assigned to have either the Day 2 or Day 4 sample taken.

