#### **4.2.2.3 Laboratory Data**

For each of the hematological and biochemical test parameters, summary statistics of observed and change from baseline values at each time point will be presented by treatment group for each scheduled time point. For laboratory parameters, post-dose observations on Day 1 will be classed as baseline.

Each observed value will be classified into three categories: Normal (for values within the normal range), High (for values higher than normal) and Low (for values lower than normal). The frequency of each category will be summarized by treatment group for each scheduled time point. Additionally, a shift table will present the changes from baseline at each scheduled time point.

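### SAP Table 5 limits Day 1 post-dose data to 0.5–4 hours while SAP 4.2.2.3 sets no limit for the laboratory baseline, so protocol-compliant baselines could be discarded

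*SAP*

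**What the plan says.** SAP 4.1.1, Table 5, is titled "Acceptable Time Windows for Parameters Other Than Data from the Patient Diary", so it covers laboratory tests. Its row for the post-dose time point at Visit 1 reads "Between 0.5 and 4 hours after dosing (on Day 1)". The text below the table says that in-window measurements "will be used for the analyses of all endpoints at each assessment time point", and adds: "The assessment time point having no measurements within the corresponding acceptable time window will be considered as missing". A footnote, beginning "if time is missing for data collected on Visit 1 where, per the schedule of activities", assigns an untimed Visit 1 measurement to the slot in which the schedule places it.

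SAP 4.2.2.3 states: "For laboratory parameters, post-dose observations on Day 1 will be classed as baseline". It gives no hours. The same section plans change-from-baseline summaries at each scheduled time point and says "a shift table will present the changes from baseline at each scheduled time point".

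The protocol's schedule of activities (Table 1) puts laboratory tests at the post-dose part of Visit 1 and on Day 6. Day 15 and Day 29 tests are conditional. It lists no pre-dose laboratory test and no clock limit for the Day 1 draw, and Protocol 8.2.3 only refers back to that schedule. The one Day 1 blood sample that the protocol does time is the PK sample in baloxavir-treated children: "One sample between 0.5 and 2 hours postdose" (Protocol Table 2).

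**The concern.** Change from baseline in laboratory results is one of the primary safety endpoints (SAP Table 1). The only planned baseline for it is the Day 1 post-dose draw, and Day 6 is the only later draw scheduled for every child. If the Day 1 value is set to missing, no other scheduled sample can serve as baseline, and the child leaves the change and shift tables for every laboratory parameter at once.

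The SAP contains two rules for this value: a general window of 0.5 to 4 hours, and a laboratory rule without hours. It does not rank them. Two programmers could follow the document faithfully and produce different primary laboratory tables.

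The window also works awkwardly for a baseline. It rejects the earliest samples, which are nearest to the untreated state, keeps later ones up to 4 hours, and keeps samples whose time is unknown.

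**Working it through.** The plan gives no figure for this point. Its only probability calculation is the chance of seeing at least one adverse event of 3% incidence among 67 children: 1 − (1 − 0.03)^67 = 87.0%, against 87% stated. It reproduces, and nothing below depends on it.

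**Step 1: the two SAP rules side by side.** Each sample below complies with the protocol's schedule.

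| Day 1 post-dose laboratory sample | If Table 5 governs | If 4.2.2.3 governs |
|---|---|---|
| 15 minutes after dosing | missing, no baseline | baseline |
| 0.5 to 4 hours after dosing | baseline | baseline |
| 5 hours after dosing | missing, no baseline | baseline |
| time not recorded | kept under the footnote, baseline | baseline |

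**Step 2: what is lost in the first and third rows.** With no pre-dose laboratory test scheduled, the child has no baseline, hence no change and no shift at Day 6 or later. The Day 1 observed value also drops out of its time-point summary. Day 6 observed values, their low/normal/high classification and the adverse event summaries remain; SAP 4.1.1 does not apply visit windows to adverse events.

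**Step 3: how many children.** This needs the distribution of draw times, which the documents do not give. As an illustration only, let f be the share of samples outside the window, assumed equal in both arms, with the planned 67 and 33 children (SAP 2.2). Baselines kept = n × (1 − f), rounded.

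| f (assumed) | Baloxavir kept (lost) | Oseltamivir kept (lost) |
|---|---|---|
| 5% | 64 (3) | 31 (2) |
| 10% | 60 (7) | 30 (3) |
| 20% | 54 (13) | 26 (7) |
| 30% | 47 (20) | 23 (10) |

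If 4.2.2.3 governs, the loss from this source is 0 in both arms at any f.

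**Step 4: could the loss differ by arm?** If laboratory and PK blood were taken together, the PK timing of 0.5 to 2 hours would place the laboratory sample inside the window, and the oseltamivir arm has no PK draw. But no section says that the draws are shared. PK sampling is planned for about 48 baloxavir children (Protocol 5 and 9.1.1), so up to about 67 − 48 = 19 may have none. Nothing indicates when oseltamivir samples are taken relative to the first dose, which is given at the site (Protocol 6.1.2). The direction and size of any difference are therefore unknown.

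**The case against.** The strongest reply is that the specific rule beats the general one. The SAP defines baseline parameter by parameter, for laboratory tests, vital signs, temperature and virology, and does so outside Table 5. The laboratory definition has no hour limit, so on an ordinary reading it governs and no child is lost. This stands to the extent that loss is not certain. A reader might infer from Table 5 alone that children will drop out of the primary laboratory analysis; the documents do not support that. The reply does not settle the matter, however. The laboratory rule speaks of the Day 1 post-dose observation, which is exactly the time point that Table 5 windows. Table 5 claims all endpoints, and nothing exempts the laboratory baseline.

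Other points on that side stand:

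- An analysis window that the protocol lacks is not a fault in itself. Protocol 9.3 expects the SAP to add technical detail.
- A reader might infer that the oseltamivir arm would lose more children. Step 4 shows that this rests on an assumption about shared draws and on PK sampling that does not cover the whole baloxavir arm.
- A reader might infer that the primary safety assessment is compromised. The study is descriptive and tests no hypothesis, and clinically significant laboratory abnormalities are still reported as adverse events. Only change and shift results are at risk, for an unknown number of children.
- Aligning the SAP's post-dose window with the protocol's 0.5 to 2 hours for PK might look tidy. Under the missing-data rule, it would discard PK samples taken between 2 and 4 hours that are now accepted.

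**Conclusion.** The point holds as an unresolved conflict within the SAP with an avoidable consequence. If the 0.5 to 4 hour window is applied to the laboratory baseline, protocol-compliant samples outside it are discarded while untimed ones are kept, and the children concerned have no change or shift result for any laboratory test. If the laboratory section governs, nothing is lost. The documents do not decide between the two.

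The number affected cannot be computed. The illustrative range of 3 to 20 of 67 and 2 to 10 of 33 rests wholly on assumed out-of-window shares of 5% to 30%, equal in both arms. Certain loss, differential loss by arm and a compromised safety conclusion all go beyond the text. The change is worth making because it concerns a primary endpoint summary with a single planned baseline draw.

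**What to change.** - In SAP Table 5 and in SAP 4.2.2.3, state that the 0.5 to 4 hour window does not apply to the laboratory baseline.
- State that any Day 1 post-dose laboratory sample qualifies as baseline and that, if there are several, the one closest to dosing is used. This also supplies the missing target time: the present tie-break picks the value nearest the target, but the row gives only a range.
- Report by arm the number of children without a laboratory baseline, so that any remaining loss or imbalance is visible.
- Leave the PK window unchanged.

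The cost is a note to one table row, a sentence or two in 4.2.2.3 and one added count per arm, all before database lock. It needs no new sample, no change to site procedures and no protocol amendment.
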